A medical event is defined within our program as “any untoward or unfavorable medical occurrence in a human research participant that occurs during the same time period the research participant is enrolled in the study and is not study related and is not serious.” It is an anticipated medical issue that is unfortunately common to individuals with chronic spinal cord injury and can occur daily, weekly monthly, or several times a year. These medical events can include urinary tract infections, kidney stones, hypotension, autonomic dysreflexia, skin sores and pressure sores with prolonged healing, joint swelling, joint soreness, joint sprain, ligament sprain, fracture, infections (non-UTI), spasticity and falls. Our standard operating procedure is that if any of these medical issues arise while directly participating in our research, if not immediately resolved, the study physician is notified and the individual is referred to the appropriate medical care. This medical care can be provided by our study physician or their colleagues or by the medical specialist of the research participant’s choice. The study physician can medically treat the issue to resolution, if appropriate, and the research participant chooses the study physician as their clinical choice for medical treatment. In this case the study physician would notify the principal investigator only if the medical issue affects their medical eligibility in the study or any of the research assessments or training paradigms. If another physician treats the medical issue the study physician will follow the individual to only assess whether the medical condition affects their medical eligibility in the study or any of the research assessments or training paradigms and will notify the principal investigator. All non-study related medical events are followed by the research team and will be reported to the IRB at the time of the continuing annual review. A weekly report of all medical events is generated by the research nurse and sent to the study physician (and physician assistant), the principal investigator, and the study physical therapists.

E. Data and Safety Monitoring Board

[name], PhD (Chair of DSMB)

Neurosurgeon, Clinical Professor

Department of Neurological Surgery

University of Miami and The Miami Project to Cure Paralysis, Miami, FL

[name]

Cardiologist, Professor of Medicine

Johns Hopkins Hospital, Baltimore, MD

[name], PhD

Urologist

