University of Zurich Spinal Cord Injury Center, Research

Balgrist University Hospital, Zurich, Switzerland

[name]
Medical Director, Spinal Cord Injury Rehabilitation
Kessler Institute for Rehabilitation, West Orange, NJ

An independent Data Safety Monitoring Board (DSMB) has been chartered to monitor the safety of research participants as well as the validity and integrity of studies conducted at the Kentucky Spinal Cord Injury Research Center, University of Louisville and the Frazier Rehab Institute. Members of the DSMB serve in an individual capacity and will convene yearly to provide their expertise including recommendations regarding the continuation, modification, or termination of any or all phases of a study. The first DSMB meeting will occur in the first quarter of the first year of the funding period and will then meet yearly after that. The DSMB will review cumulative study data to evaluate safety, study conduct, scientific validity and data integrity. DSMB members may review current versions of the protocol and Informed Consent Form, and any subsequent amendments to ensure an understanding of a study's objectives and design. Day-to-day oversight of the study will be provided by the Principal Investigators. They will review all study data and any adverse events, and report all adverse events to the IRB and DSMB chairperson as appropriate. Medical events that occur while the research participants are engaged in the research protocols also will be logged by a research nurse, research physical therapists, study physicians and/or research staff. Any adverse events are collected on an Adverse Event Form and will be reported at the yearly DSMB meeting. An Adverse Event report will be generated for each event and will include a description of the event, when and how it was reported, as well as any official chart records or documentation to corroborate the event and a determination of attribution. Any Adverse Event that the principal investigator determines to be definitely, probably, or possibly related to the research intervention, or serious in nature, and unexpected will be reported to the IRB within 5 business days of the principal investigator gaining knowledge of the event. Any unanticipated problems involving risks to research participants or others will include a corrective plan and measures to prevent reoccurrence. Such events will be reported to appropriate regulatory agencies as required within 5 business days of the principal investigator gaining knowledge of the event.

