Appendix #2

Medical Event Reporting Unrelated to the Research Protocol Version 2, 12/12/2016

A medical event is defined within our program as any untoward or unfavorable medical occurrence in a human research participant that occurs during the enrollment period of a study.

As the team is made aware of study participants' medical events, they will be recorded in a log for tracking and reporting.

Medical events that occur during a research visit will be reported to the study nurse and then elevated to the study physician if not immediately resolved. The physician will evaluate these medical events, to determine causality with relation to the research and referral for medical care.

A weekly report of all medical events is generated by the research nurse and sent to the study physician (and physician assistant), the principal investigator, the regulatory core, and the study therapists for review of causality and follow-up.

We have developed a table outlining the most common expected events in the spinal cord injury (SCI) population. These events occur with this population on a frequent basis. This table will allow the IRB and our staff to understand how expected and unrelated events will be documented and reported.

If a physician outside the study team treats the medical event, the study physician will follow the event to assess the following:

- The medical condition affecting their medical eligibility for research
- Determination on causality of the event
- The event's effect on research assessments and/or training paradigms

All conclusions reached by the study physician will be reported to the PI.

Characteristics of Medical Events in the Spinal Cord Injury Population (Unrelated to Study)					
Medical Event	Probability	Medical Event Severity	Medical Intervention	Serious Event	Reporting
Urinary Tract Infections	Likely	Mild	Antibiotics	No	Research Medical Log
	Likely	Moderate	Antibiotics	No	Research Medical Log
	Rare	Moderate	Hospitalization	No	IRB Continuation Review
	Rare	Severe	Hospitalization	Yes	IRB Continuation Review
Urinary Tract Infections that significantly interfere with research conduct	Rare	Moderate	Depends on specific diagnosis	No	IRB Continuation Review
	Rare	Moderate	Hospitalization	No	IRB Continuation Review
	Rare	Moderate	Hospitalization	Yes	IRB Continuation Review
Urinary Tract Infection/Kidney	Less Likely	Moderate	Depends on specific diagnosis	No	Research Medical Log
	Rare	Moderate	Hospitalization	No	IRB Continuation Review

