	Rare	Severe	Hospitalization	Yes	IRB Continuation Review
Urinary Tract Infections/Kidney that significantly interfere with research conduct	Rare	Moderate	Depends on specific diagnosis	No	IRB Continuation Review
	Rare	Moderate	Hospitalization	No	IRB Continuation Review
	Rare	Severe	Hospitalization	Yes	IRB Continuation Review

Characteristics of Medical Events in the Spinal Cord Injury Population (Unrelated to Study)					
Medical Event	Probability	Medical Event Severity	Medical Intervention	Serious Event	Reporting
Kidney Stones	Less Likely	Moderate	Depends on specific diagnosis	No	Research Medical Log
	Rare	Moderate	Hospitalization	No	IRB Continuation Review
	Rare	Severe	Hospitalization	Yes	IRB Continuation Review
Kidney Stones – significantly interferes with research conduct	Rare	Moderate	Depends on specific diagnosis	No	IRB Continuation Review
	Rare	Moderate	Hospitalization	No	IRB Continuation Review
	Rare	Severe	Hospitalization	Yes	IRB Continuation Review

Characteristics of Medical Events in the Spinal Cord Injury Population (Unrelated to Study)					
Medical Event	Probability	Medical Event Severity	Medical Intervention	Serious Event	Reporting
Hypotension	Likely	Mild	None	No	None
	Rare	Moderate	Physician Referral	No	Research Medical Log
	Rare	Moderate	Depends on specific diagnosis; includes medication and/or hospitalization	No	IRB Continuation Review
	Rare	Severe	Depends on specific diagnosis; includes medication and/or hospitalization	Yes	IRB Continuation Review
Hypotension that interferes with research conduct	Less Likely	Moderate	Cease stand or step; Elevate legs above heart	No	None
	Rare	Moderate	Physician Referral	No	Research Medical Log
Hypotension that significantly interferes with research conduct	Rare	Moderate	Depends on specific diagnosis; includes medication and/or hospitalization	No	IRB Continuation Review
	Rare	Severe	Depends on specific diagnosis; includes medication and/or hospitalization	Yes	IRB Continuation Review

Characteristics of Medical Events in the Spinal Cord Injury Population (Unrelated to Study)					
Medical Event	Probability	Medical Event Severity	Medical Intervention	Serious Event	Reporting
Autonomic Dysreflexia	Likely	Mild	None	No	None
	Less Likely	Moderate	Identify and eliminate source	No	None
	Rare	Moderate	Depends on specific diagnosis; includes medication and/or hospitalization	No	IRB Continuation Review
	Rare	Severe	Depends on specific diagnosis; includes medication and/or hospitalization	Yes	IRB Continuation Review

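### Appendix #2 codes the same hospitalised event as both serious and not serious, and keeps events it marks serious in a class that section IV.D defines as not serious

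*Protocol*

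**What the plan says.** Protocol section IV.D (Medical Events Unrelated to the Study) defines a medical event as an unfavourable occurrence while the participant "is enrolled in the study and is not study related and is not serious". Such events are followed by the team and reported to the IRB at annual continuing review.

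Appendix #2 gives a different definition: "any untoward or unfavorable medical occurrence in a human research participant that occurs during the enrollment period of a study". It then tabulates common events by probability, severity, intervention, seriousness and reporting, and states the purpose: "This table will allow the IRB and our staff to understand how expected and unrelated events will be documented and reported".

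In the block headed "Urinary Tract Infections that significantly interfere with research conduct", one row reads "Rare Moderate Hospitalization No IRB Continuation Review" and the next reads "Rare Moderate Hospitalization Yes IRB Continuation Review". Elsewhere the usual serious hospitalisation row reads "Rare Severe Hospitalization Yes IRB Continuation Review".

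Section IV.E puts adverse events on an Adverse Event Form and takes them to the yearly DSMB meeting. Its expedited rule covers events that the principal investigator judges related to the intervention, "or serious in nature, and unexpected will be reported to the IRB within 5 business days".

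Section IV.C.2.b (Epidural Stimulation) lists autonomic dysreflexia and sustained rises or falls in blood pressure among its examples of serious adverse effects of stimulation.

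**The concern.** Staff are to use this table to decide how an event is recorded. Three things go wrong if they follow it as written.

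- For one event type the table gives two opposite seriousness codes, with nothing to choose between them.
- The class of medical events excludes serious events in section IV.D but includes them in Appendix #2. An event marked serious can then stay in the medical-event log, with IRB continuation review as its only listed reporting, instead of going on the Adverse Event Form and to the DSMB.
- Seriousness is treated as a grade of severity. Nothing in the protocol text reviewed defines serious, so nothing corrects the table.

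Participants receive a surgical implant, and half start stand training in the first intervention period. Section IV.B lists falls, broken bones, blood pressure changes, urinary tract infection and dysreflexia among the risks of study assessments and training. The same kinds of event appear in Appendix #2 as unrelated. A clean count of serious events, with a causality decision for each, is what the DSMB needs to tell the two apart.

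**Working it through.** No sample size, power or error rate is involved. The check is a count of the Appendix #2 rows and a comparison of sections.

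**Row count.** The table has 80 rows. Those that name hospitalisation divide as follows.

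| Intervention column | Serious = No | Serious = Yes |
|---|---|---|
| Hospitalisation alone | 14 (12 Moderate, 2 Moderate - Reoccurs) | 14 (13 Severe, 1 Moderate) |
| Includes medication and/or hospitalisation | 4 (all Moderate) | 4 (all Severe) |
| Total | 18 | 18 |

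The 14 come from seven event families with two rows each: urinary tract infection, urinary tract infection/kidney, kidney stones, skin sores, non-urinary infections, falls and spasticity (7 × 2 = 14). The 4 are hypotension (2) and autonomic dysreflexia (2). So 14 + 4 = 18 of the 36 rows that name hospitalisation are coded not serious, and all 18 are graded moderate.

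**All serious rows.** To the 18 in the right-hand column add 4 whose intervention depends on the diagnosis: 2 skin sore rows and 2 fracture or orthopaedic injury rows. 18 + 4 = 22 rows are Serious = Yes. All 22 give IRB continuation review as the reporting.

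**Identical rows with opposite codes.** A search within each event block for rows that match on severity, intervention and reporting but differ on seriousness finds exactly one pair: the two urinary tract infection rows quoted above. They also share the same probability. In the other 13 blocks that pair a No and a Yes row for hospitalisation alone, the Yes row is graded Severe. The column therefore tracks severity everywhere except in this pair. In the two fracture rows the word Serious is itself entered as the severity grade, which shows the two concepts being merged.

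**Sections side by side.**

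- Section IV.D: a medical event is unrelated and not serious. Appendix #2: its definition omits the not-serious limit, and the table contains 22 serious rows. Both cannot stand.
- Section IV.E: adverse events go on the Adverse Event Form and to the DSMB. Appendix #2: no row, serious or not, names either.
- Section IV.C.2.b: dysreflexia and sustained blood pressure change are examples of serious adverse effects when stimulation causes them. Appendix #2: moderate dysreflexia or hypotension that needs medication and/or hospitalisation is not serious. The first concerns related events and the second unrelated ones, so this is not a strict contradiction. It does mean that the seriousness of the same clinical picture changes with its attribution.

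**The case against.** The strongest reply is that this is a table of expected, unrelated events with safeguards around it. Much of that stands.

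- *Attribution.* A reader might infer that Appendix #2 drops the unrelated condition as well. It does not. The condition is missing from the one-sentence definition but is kept in the appendix title, the table headers and the sentence on the table's purpose. The appendix also requires the study physician to determine causality and provides a weekly report for causality review. The gap is in seriousness and routing, not in the absence of a causality step.
- *Expedited reporting.* A reader might infer that the coding keeps events out of the 5-business-day rule. That is not shown. The rule also requires the event to be unexpected, and the table lists expected events. Recoding a row may change nothing there, and events judged related have their own limb.
- *Visibility to the IRB.* All 36 rows that name hospitalisation, whether No or Yes, reach the IRB at continuing review. The classification and the count suffer, not the IRB's eventual knowledge of the event.
- *DSMB.* Section IV.E does not make DSMB review depend on the Serious Event column, and the DSMB reviews cumulative study data. What keeps these events off the stated form is the medical-event label.
- *Convention.* That hospitalisation makes an event serious is the usual safety criterion, but the protocol does not say so. Without it, the 18 rows coded No are an unexplained scheme rather than a contradiction.
- *Typing slip.* The odd row is probably meant to read Severe. As written it still gives two answers.

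The duplicate row, the conflict with section IV.D and the routing of the 22 serious rows do not depend on the convention, and none of these replies removes them.

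**Conclusion.** The appendix is wrong as written. It contains one directly contradictory pair of rows, 22 serious rows inside a class that section IV.D defines as not serious, and 18 moderate rows that involve or may involve hospitalisation coded not serious. The first two rest on the text alone. The third becomes an error only on the assumption that hospitalisation is a criterion for seriousness.

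The consequence is that serious events can be under-counted in the safety record, and that events the table itself calls serious can stay off the Adverse Event Form and DSMB route. A reader might go further and conclude that serious harms are under-counted. The protocol does not support that: it contains no event data, and its physician causality review may redirect some events. The direction is reasonable to expect, but the size cannot be derived. Randomisation, endpoints and efficacy analysis are not touched.

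**What to change.** 1. State one definition of serious, independent of severity and used throughout the protocol. Hospitalisation is the usual criterion. Recode the 18 rows to that definition, and remove Serious as a severity grade in the two fracture rows.
2. Reconcile the two conflicting urinary tract infection rows. Do not simply delete one, because that could remove the block's only serious entry.
3. Align the definition of a medical event in section IV.D and Appendix #2, and reconcile the dysreflexia and hypotension rows with section IV.C.2.b.
4. Enter every Serious = Yes event on the Adverse Event Form and in the DSMB report, with the causality decision that Appendix #2 already requires.

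The cost is an edit to the appendix and the matching reporting text, plus somewhat more adverse-event paperwork. The trial design does not change.

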- Skin irritation from adhesive tape, sensors, wires, and/or pads
- Tingling feeling from the stimulation
- Dizziness by breathing in and out hard
- Dizziness during sitting, standing or stepping
- Skin irritation from vein needle and/or fine wire insertion
- Slight discomfort from the pressure of the ultrasound probe
- Skin irritation from ECG sensor placement

Less Likely

- Bleeding and/or bruising from fine wire insertion and/or blood draw
- Pain and/or infection from blood draw
- Skin abrasion from hand placement of trainers

- Feelings of claustrophobia
- Shortness of breath
- Significant changes in heart rate and/or blood pressure
- Muscle and joint soreness

Rare

- Chest pain
- Joint sprain
- Nausea
- Fall
- Broken bones requiring medical treatment
- Broken bones requiring surgical treatment and long-term medical follow-up

Risks of Bladder Assessments

Likely

- Feeling of shyness
- Significant changes in heart rate or blood pressure
- Autonomic dysreflexia symptoms that resolves when the cause is removed

Less Likely

- Mild discomfort, especially during urination after Urodynamics
- Urinary tract infection requiring oral antibiotics
- Discomfort from lying still for ultrasound

Rare

- Autonomic dysreflexia symptoms but the cause cannot be identified and the high blood pressure does not resolve and medical intervention is required
- Urinary tract infection requiring intravenous antibiotics
- Excessive pain, fever, chills

Risks of Bowel Assessments

Likely

- Feeling of shyness
- Significant changes in heart rate or blood pressure
- Autonomic dysreflexia that resolves when the cause is removed

Rare

- Autonomic dysreflexia symptoms but the cause cannot be identified and the high blood pressure does not resolve and medical intervention is required
- Bleeding of the rectum
- Bowel infection requiring oral antibiotics
- Bowel perforation in those with previous rectal surgery, bowel inflammation, or bowel obstruction

Risks of Sexual Function Assessments (Questionnaires)

Likely

- Feeling of shyness

Risks of Stand and Voluntary Training Interventions

Likely

- Skin irritation from hand placements of trainers
- Skin irritation from adhesive tape, sensors, wires, and/or pads
- Dizziness during sitting, standing, or stepping
- Skin irritation from fine wire insertion

Less Likely

- Bleeding and/or bruising from fine wire insertion
- Skin abrasion from hand placements of trainers
- Shortness of breath

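### Section IV.D sends all unrelated medical events to the IRB each year, but Appendix #2 stops 28 of its 80 lines at a log or at 'None', including every line rated 'Likely'

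*Protocol*

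**What the plan says.** **Section IV.D (Medical Events Unrelated to the Study).** A medical event here is one that "is not study related and is not serious". The section gives examples: "These medical events can include urinary tract infections, kidney stones, hypotension, autonomic dysreflexia, skin sores and pressure sores with prolonged healing", followed by joint problems, fracture, other infections, spasticity and falls. Its reporting rule has no exceptions: "All non-study related medical events are followed by the research team and will be reported to the IRB" at the annual continuing review.

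**Appendix #2.** The definition is wider, "any untoward or unfavorable medical occurrence in a human research participant that occurs during the enrollment period of a study", and carries no limit to non-serious events. The text says that events the team learns of will be recorded in a log. It introduces its table with the words "This table will allow the IRB and our staff to understand how expected and unrelated events will be documented and reported". The table then gives each line a probability rating, a severity, an intervention, a serious flag and one of three reporting outcomes: 'None', 'Research Medical Log' or 'IRB Continuation Review'. A weekly report of all medical events goes to the study physician, the principal investigator, the regulatory core and the therapists. Neither the IRB nor the DSMB is named as a recipient.

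**Section IV.E (DSMB).** The DSMB meets yearly and reviews cumulative study data for safety. On event data the text says: "Any adverse events are collected on an Adverse Event Form and will be reported at the yearly DSMB meeting". Medical events are said to be logged. The section does not say that the log goes to the DSMB.

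**Section IV.B (Potential Risks).** Some of the same event types are also listed as risks of study procedures, for example "Urinary tract infection requiring oral antibiotics" under bladder assessments and falls under stand and voluntary training.

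**The concern.** Two parts of one protocol fix different rules for the same events, and I found no statement of which one governs. Staff who follow the appendix will not do what IV.D promises.

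The lines that drop out are the frequent ones. When an event is common in this population anyway, an effect of stimulation or training on it shows mainly as a change in frequency. It is hard to see in a causality judgement made one case at a time, because each single urinary infection or fall has a ready background explanation. Aggregate counts are the natural way to see such a change.

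Two of the 'None' entries bear directly on the interventions:

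- Hypotension that interferes with research and is handled by stopping standing or stepping. Stand training is what separates Group B from Group A in the first intervention period.
- Autonomic dysreflexia, in its mild and in its source-removed moderate form. IV.C.2.b names dysreflexia as a possible serious adverse effect of stimulation.

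**Working it through.** The protocol states no figure to reproduce. The check is a line count of the Appendix #2 table, set against the rule in IV.D.

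**Step 1. Count by event family.** Each family includes its sub-entries for interference, infection or fracture.

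| Event family | IRB | Log only | None | Lines |
|---|---|---|---|---|
| Urinary tract infection | 5 | 2 | 0 | 7 |
| Urinary tract infection/kidney | 5 | 1 | 0 | 6 |
| Kidney stones | 5 | 1 | 0 | 6 |
| Hypotension | 4 | 2 | 2 | 8 |
| Autonomic dysreflexia | 5 | 0 | 2 | 7 |
| Skin sore | 8 | 4 | 2 | 14 |
| Joint soreness with swelling | 5 | 2 | 1 | 8 |
| Infections (non-UTI) | 5 | 2 | 1 | 8 |
| Falls | 5 | 2 | 1 | 8 |
| Spasticity | 5 | 1 | 2 | 8 |
| **Total** | **52** | **17** | **11** | **80** |

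Lines that do not reach the IRB: 17 + 11 = 28, and 28/80 = 35%.

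**Step 2. Count by the table's own probability rating.**

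| Rating | IRB | Log only | None | Lines |
|---|---|---|---|---|
| Likely | 0 | 4 | 9 | 13 |
| Less Likely | 5 | 11 | 2 | 18 |
| Rare | 47 | 2 | 0 | 49 |

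No 'Likely' line reaches the IRB, against 47 of 49 'Rare' lines.

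**Step 3. Do the 28 lines fall under the IV.D rule?** IV.D covers non-serious events. The table flags 22 lines as serious, and all 22 go to the IRB. That leaves 80 − 22 = 58 non-serious lines. All 28 lines kept from the IRB are among them, so each lies within IV.D's definition and 28/58 = 48% of the lines it covers depart from its rule. The 22 serious lines are a separate, smaller mismatch, since IV.D's definition excludes serious events and the appendix includes them.

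**Step 4. What sort of events are the 28?** Every line whose intervention is simply hospitalisation goes to the IRB. So does every line for urinary infections, stones, sores and falls that interfere with the research. Two of the 28 lines are for hypotension that interferes with research: one handled by stopping standing or stepping ('None') and one by physician referral (log). The other 28 − 2 = 26 involve neither hospitalisation nor stated interference. Examples are urinary infections given antibiotics, sores referred to wound care, stones not hospitalised and falls referred to a physician.

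**Step 5. Is 'None' unrecorded?** The appendix text says medical events are recorded in a log. If that holds for all of them, 'None' can only mean no onward report. If 'None' is read literally, those events are not even logged, which contradicts the appendix's own text. The table should not leave this open.

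**The case against.** A reader might infer that common events under stimulation are seen by no oversight body, that the DSMB receives adverse events and nothing else, or that the DSMB is unable to detect a rise. The protocol does not support any of these. IV.E does not say that adverse events are all the DSMB receives. It gives the DSMB a review of cumulative study data, and the contents of its data package may be set in a charter that is not at hand. An event judged related leaves the unrelated-events table, becomes an adverse event and goes to the yearly DSMB meeting. IV.D, if it governs, sends every unrelated event to the IRB.

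Other points on that side also stand:

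- The count is of table lines, not of events. It depends on how severity and intervention were split and does not measure lost safety information.
- The weekly report is reviewed for causality, so the team itself sees the events. IV.C.2.b also has a pattern-level trigger for re-evaluating stimulation, though it is operated by the research team and concerns serious effects.
- Some comparisons would be weak. Appendix #1 gives urodynamics on one schedule for everyone, so it creates no contrast between groups. Stand training is a randomised contrast only in the first intervention period, 18 against 18, because Group A then crosses over.
- Sending counts to the DSMB goes beyond IV.D, which promises IRB reporting only.

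None of this removes the conflict between IV.D and the table. Nor does any of it expressly commit the protocol to passing on aggregate counts of events judged unrelated.

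**Conclusion.** The contradiction is real and lies within the protocol: IV.D says all, and Appendix #2 omits 28 of 80 lines, including all 13 rated 'Likely'. What follows for safety monitoring is conditional. If staff follow Appendix #2, no part of the protocol expressly commits to sending the IRB or the DSMB counts of these common events when each is judged unrelated, so a rise in their rate under stimulation or stand training could be missed. That falls short of saying it would be missed, since the DSMB's remit leaves room for such data.

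The conclusion assumes that the table is meant to be followed as written and that no charter already supplies the counts. The protocol gives no background event rates, so the chance of missing a given rise cannot be calculated. The point is worth correcting, but it does not touch the efficacy analyses.

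**What to change.** 1. Reconcile IV.D and Appendix #2 so that every medical event is logged and reaches the IRB at annual review, as IV.D states. Replace 'None' and 'Research Medical Log' as end points accordingly, and align the two definitions on whether serious events are included.
2. State in IV.E that the DSMB's cumulative data include the log's yearly counts for each Appendix #2 event type, by randomised group (A1, A2, B1, B2) and study phase, irrespective of attributed causality. Show participant time beside the counts, because phases differ in length. Comparisons between phases need caution, because contact with the team, and so the chance of hearing of an event, differs between Usual Care and the interventions.

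The cost is one extra summary table a year, drawn from a log and a weekly report that already exist, plus logging of any 'None' events not now recorded. No treatment, assessment or clinical rule changes.
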